Malnutrition is common among cancer patients, with prevalence rates ranging from 16–40% at diagnosis and increasing to 40–80% during treatment, depending on factors such as age, cancer type, and treatment modality(Bossi *et al*, 2021; Kaegi-Braun *et al*, 2021). Tumor location plays a crucial role, with the highest malnutrition rates observed in pancreatic (66.7%), esophageal/gastric (60.2%), head and neck (48.9%), and lung (45.3%) cancers(Hébuterne *et al*, 2014; Bossi *et al*, 2021).

Nutritional status in cancer patients is intricately linked to clinical outcomes. Tumor and therapeutic interventions notably impact nutritional health(Webb *et al*, 2020; Kipouros *et al*, 2023). Malnutrition significantly affects treatment tolerance, morbidity, survival, and quality of life(Hébuterne *et al*, 2014; Liu *et al*, 2021; Garutti *et al*, 2023). It can lead to reduced nutrient intake, cachexia, and impaired treatment efficacy(Muscaritoli *et al*, 2019; Holdoway *et al*, 2023). Early nutritional interventions have been shown to mitigate adverse clinical outcomes and reduce 30-day mortality in at-risk patients(Muscaritoli *et al*, 2019; Schuetz *et al*, 2019; Kipouros *et al*, 2023).

Although the association between malnutrition and adverse clinical outcomes has been well established (Muscaritoli *et al*, 2019; Liu *et al*, 2021; Kipouros *et al*, 2023), the benefits of nutritional improvement reported in different studies remain inconsistent (Schuetz *et al*, 2019; Kaegi-Braun *et al*, 2021). On the one hand, nutritional status might vary considerably over the course of treatment(Webb *et al*, 2020); on the other hand, psychological factors, sleep quality, and physical activity may further influence these outcomes (Nissim *et al*, 2024; Ye *et al*, 2024). High-quality and large-scale cohort studies that can capture dynamic changes in nutrition are needed to carry out more precise nutritional interventions or treatments to improve clinical outcomes. Hence, we established a cohort study to evaluate nutritional status and clinical outcomes in patients with common malignancies (NCOM study), aiming to provide evidence for personalized and precise nutritional treatment in oncology care.

53 **Methods**

54 **Study design**

55 The NCOM study is a multicenter, prospective cohort study designed to assess longitudinal
56 changes in nutritional status and their impact on clinical outcomes in cancer patients. We aim

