The sample size for the NCOM study was determined on the basis of the impact of nutritional status on clinical outcomes in cancer patients, with a two-sided significance level (α) of 0.05 and 80% power ($1 - \beta = 0.80$) (von Elm *et al*, 2007; Arends *et al*, 2017). On the basis of previous studies on nutritional status and cancer outcomes, we assumed a baseline event rate of 20% ($P_1 = 0.50$) in the unexposed group and an expected rate of 24% ($P_2 = 0.40$) in the exposed group (Rasschaert *et al*, 2024). Given that longitudinal oncology cohort studies report attrition rates ranging from 30% to 50% over a multiyear follow-up period (Reeves *et al*, 2007; Schwedhelm *et al*, 2016), the final target sample size for this study was estimated to be approximately 1,538 participants.

Data collection

Data collection followed a standardized protocol across all participating hospitals to ensure consistency and accuracy. The baseline assessments will be conducted within 48 hours of hospital admission, and well-trained researchers will collect information on demographic and clinical data, nutritional status, laboratory biomarkers, quality of life, psychosocial factors, physical activity, sleep status, and knowledge, attitudes, and practices (KAPs). Follow-up assessments will be conducted at predefined intervals to track longitudinal changes in nutritional status and clinical outcomes.

To ensure data reliability, each hospital will designate 1 to 2 trained personnel to be responsible for questionnaires and clinical data recording. At the same time, a supervisor will be appointed to review the integrity of the data and coordinate follow-up work if necessary. All researcher personnel

must complete standardized training and pass competency assessments to ensure consistency in data collection and minimize variations.

Data management will be centralized through the Research Electronic Data Capture (REDCap) system, which ensures data security, accuracy, and accessibility(Harris *et al*, 2009). Standardized, validated measurement tools will be used at each site. Data entry will include built-in validation checks to identify missing values or inconsistencies, with routine audits and cross-site comparisons performed to maintain high data quality and study validity.

Data Content & Assessment Tools

Demographics & Clinical Data

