Upon enrollment, trained personnel will obtain informed consent and record demographic details, including sex, age, marital status, occupation, education, and socioeconomic status. Lifestyle factors such as smoking, alcohol, and tea consumption are documented, given their potential influence on nutritional status and cancer progression(Yuan *et al*, 2023). Medical history, including chronic conditions, previous diagnoses, medication use, and family history of malignancies, will also be recorded to assess genetic predispositions.

Cancer-specific data will be collected at baseline and updated at follow-ups to monitor disease progression and treatment response. This includes pathology-confirmed diagnosis, TNM staging at first diagnosis, and available molecular markers. The tumor burden will be reassessed at each visit, alongside major treatments (surgery, chemotherapy, radiotherapy, targeted therapy, and immunotherapy), with details on the type, duration, and response. Nutritional support, including enteral or parenteral nutrition in the preceding week, will be tracked to evaluate its impact on treatment outcomes.

Karnofsky Performance Status (KPS): The KPS evaluates a patient's ability to perform daily activities, the presence of physical discomfort, and overall performance status, providing a standardized measure of functional impairment(McNair *et al*, 2023).

Nutritional assessments

Nutritional assessments will be conducted via validated screening tools to evaluate nutritional status, risk factors, and dietary intake patterns. Two primary tools and standardized anthropometric

measurements will be employed to assess malnutrition risk and severity:

Subjective Global Assessment (mPG-SGA): The mPG-SGA scoring system consists of five sections: weight loss history, dietary intake changes, symptoms, activity and function levels, and age. Patients' nutritional status will be categorized on the basis of scores as normal (0–2 points), mild malnutrition (3–6 points), and moderate malnutrition (≥ 7 points)(Huo *et al*, 2023a). The version used in this study, mPG-SGAL11, is an adapted and validated version developed for Chinese cancer patients who that incorporates modifications on the basis of nationwide clinical feedback and statistical validation(Fu *et al*, 2022; Huo *et al*, 2023b).

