Nutrition support in and out of hospital Nutrition support	√	√	√	√	√	√	√
Laboratory biomarkers	√	√	√	√	√	√	√
EORTC QLQ-C30	√	√	√	√	√	√	√
HADS	√	√	√	√	√	√	√
PSQI	√	√	√	√	√	√	√
Leisure-time physical activity levels	√	√	√	√	√	√	√
KAP Questionnaire	√				√	√	√
Short-Term Clinical Outcome		√	√	√	√	√	√
Long-term clinical outcomes		√	√	√	√	√	√
Adverse Event Recording	√	√	√	√	√	√	√

299 **Table 1.** Follow-up schedule. SV: screening visit; KPS: Karnofsky Performance Status; mPG-SGA:
 300 Subjective Global Assessment; NRS-2002: Nutritional Risk Screening 2002; SDSAT: Simple Diet Self-
 301 Assessment Tool; EORTC QLQ-C30: European Organization for Research and Treatment of Cancer

Quality of Life Questionnaire C30; HADS: Hospital Anxiety and Depression Scale; PSQI: Pittsburgh Sleep Quality Index; KAP : Knowledge, Attitude, and Practice.

Statistical analysis plan

Baseline characteristics are summarized as the means \pm standard deviations (SDs) for normally distributed variables, medians with interquartile ranges (IQRs) for skewed data, and percentages for categorical variables. For group comparisons (e.g., normal vs. mild malnutrition vs. moderate malnutrition patients), independent t tests or Mann–Whitney U tests were used for continuous variables, and chi–square tests or Fisher’s exact tests were used for categorical data.

The primary outcome analysis will apply multivariate regression models, adjusting for age, sex, cancer stage, treatment modality, socioeconomic status, and baseline Karnofsky Performance Status (KPS). Logistic regression was used to assess binary outcomes (e.g., nutritional risk, survival), whereas linear regression was used to evaluate continuous variables (e.g., BMI changes, weight loss percentage). To account for repeated measures, generalized estimating equations (GEEs) model longitudinal variations in nutritional status, biomarkers, and quality of life.

For survival analysis, Kaplan–Meier curves were used to estimate overall survival (OS) and progression-free survival (PFS), with log-rank tests used to compare groups. Cox proportional hazards models were used to explore the associations between nutritional status and survival outcomes, incorporating time-dependent covariates where applicable.

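### The 1,538 target has 80% power only with two equal exposure groups, which the protocol neither states nor secures; toward the ends of its own malnutrition range, power falls to about 54–61%

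*Protocol*

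**What the plan says.** The Sample size section plans for a "two-sided significance level (α) of 0.05 and 80% power". It compares one unexposed with one exposed group, giving a "baseline event rate of 20% ($P_1 = 0.50$) in the unexposed group" and "an expected rate of 24% ($P_2 = 0.40$) in the exposed group". It cites "attrition rates ranging from 30% to 50% over a multiyear follow-up period" without choosing a value, and concludes that "the final target sample size for this study was estimated to be approximately 1,538 participants". It gives no ratio of group sizes and does not define exposed.

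Elsewhere in the protocol:

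- The Introduction reports malnutrition "prevalence rates ranging from 16–40% at diagnosis and increasing to 40–80% during treatment", and site-specific rates of 66.7% (pancreatic), 60.2% (esophageal/gastric), 48.9% (head and neck) and 45.3% (lung).
- Study design makes nutritional status the primary exposure. The Recruitment strategy and the eligibility criteria set no quota by nutritional status.
- Nutritional assessments divides the mPG-SGA into "normal (0–2 points), mild malnutrition (3–6 points), and moderate malnutrition (≥ 7 points", and gives a two-level cut for the NRS-2002 at a score of 3.
- The Statistical analysis plan section opens with baseline summaries and writes there: "For group comparisons (e.g., normal vs. mild malnutrition vs. moderate malnutrition patients". The primary outcome analysis comes in the next paragraph as adjusted regression, without saying how exposure is coded.

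**The concern.** In a randomised trial the investigator sets a 1:1 ratio. In this cohort the ratio is whatever share of enrolled patients turns out to be malnourished. The printed target reproduces only with a 1:1 ratio, so the 80% depends on an assumption that the reader cannot see and that much of the protocol's own prevalence range does not meet. If most patients are assessed near diagnosis, the exposed group may be too small. If most are well into treatment, the well-nourished reference group may be too small.

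What is at stake is how a null result is read. A finding of no association would be judged against 80% power when the design may have had nearer 55–60%.

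**Working it through.** **Inputs.** From the Sample size section: two-sided alpha 0.05 (z = 1.960), power 80% (z = 0.8416), rates 0.50 and 0.40 (the symbols) or 0.20 and 0.24 (the words), attrition 30–50%. From the Introduction: exposed share f from 16% to 80%. Assumption: attrition is the same in both groups.

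**Step 1: reproduce 1,538.** With unpooled variance and equal groups:

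n per group = (1.960 + 0.8416)² × (0.50 × 0.50 + 0.40 × 0.60) / 0.10² = 7.849 × 0.49 / 0.01 = 384.6

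Enrolled = 2 × 384.6 / (1 − 0.50) = 1,538.4

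This matches the printed figure. The pooled-variance formula gives 388 per group and 1,552 enrolled, which is close. At 30% attrition the unpooled formula gives about 1,099, which does not match. So 1,538 implies 0.50 vs 0.40, equal groups and 50% attrition.

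**Step 2: power by exposed share.** With N evaluable patients:

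Power = Φ( 0.10 / √[0.25 / ((1 − f)N) + 0.24 / (fN)] − 1.96 )

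Example with N = 769 and f = 0.16 (123 exposed, 646 unexposed): the standard error is 0.04835, 0.10 / 0.04835 = 2.068, and Φ(0.108) = 54%.

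| Exposed share | 50% attrition (N = 769) | 30% attrition (N ≈ 1,077) |
|---|---|---|
| 16% | 54% | 69% |
| 20% | 62% | 76% |
| 30% | 73% | 86% |
| 40% | 79% | 90% |
| 50% | 80% | 91% |
| 60% | 78% | 90% |
| 66.7% | 75% | 88% |
| 80% | 61% | 75% |

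Pooled variance changes the N = 769 figures by about one point.

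**Step 3: detectable difference at 80% power, N = 769.** This is 2.8016 times the standard error, with the variances held at their planned values:

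- f = 0.50: about 10.0 points
- f = 0.16: 2.8016 × 0.04835 = 0.1355, about 13.5 points
- f = 0.80: 2.8016 × 0.0449 = 0.1258, about 12.6 points

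**Step 4: the worded rates.** With 0.20 vs 0.24, n per group = 7.849 × (0.16 + 0.1824) / 0.04² ≈ 1,680, or about 6,720 enrolled after 50% attrition. With 769 evaluable in equal groups, power is about 27%. The two pairs of rates also point in opposite directions: exposed patients do worse in the words and better in the symbols, if an event is adverse.

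**Step 5: three classes, for scale only.** With equal thirds of 769 (about 256 each) and a 10-point difference, one pairwise comparison has about 63% power. Searching over unequal splits finds none that raises the weakest of the three pairs above this. An illustrative 60/25/15 split gives 66% (normal vs mild), 50% (normal vs moderate) and 41% (mild vs moderate), each taken separately at 10 points.

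**The case against.** Several stronger readings are tempting, and the protocol does not support them.

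- **That the cited malnutrition rates are far from 50%.** Several are not. Shares of 40%, 45.3%, 48.9% and 60.2% give 79%, 80%, 80% and 78% power. The rates are also literature ranges and not a forecast of this cohort's case mix. This part of the objection stands: the loss is material toward 16–30% and from about 67% upward.
- **That only equal groups reach 80%.** This is true only at 50% attrition, the top of the cited range. At 30% attrition, shares of 25–75% give about 81–91%. At 40% attrition (923 evaluable), shares of 30–67% give about 81–87%. The objection stands as a limit on size. Even at 30% attrition the extremes fall short, with 69% at 16% exposed and 75% at 80%.
- **That the planned analysis is a three-class mPG-SGA comparison promised 80% power.** The three classes appear as an example beside the baseline summaries. The sample size is written for two groups, a two-level NRS-2002 cut exists, and the coding of exposure may properly be left to a statistical analysis plan.
- **That every class comparison has at most 63% power.** That figure bounds only the weakest pair; the 60/25/15 split already gives 66% for normal vs mild. Three classes also cannot all differ pairwise by exactly 10 points. With illustrative rates of 0.50/0.40/0.30, normal vs moderate differs by 20 points and is well powered.

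None of this supplies the missing group ratio. The protocol prints an N and a power that depend on it, so this is not a detail that a later document would merely fill in.

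**Conclusion.** The point holds in a limited form. The stated 80% power is correct arithmetic for 0.50 vs 0.40, two equal groups and 50% attrition. The equal split is unstated, and an observed exposure does not secure it. Over the protocol's own 16–80% range, power at 769 evaluable is about 54–80%. The loss is 2 points or less between 40% and 60% exposed, about 26 points at 16% and about 19 points at 80%. With lower attrition it shrinks to the ends of the range.

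These figures accept the rates in symbols and equal attrition in both groups. They cannot stand as the protocol's power until the worded rates are reconciled with the symbols, since the worded rates give about 27% even with equal groups. A reader should not infer that the study is underpowered at every plausible case mix, or that the protocol claims 80% power for pairwise mPG-SGA comparisons.

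**What to change.** Revise the Sample size section in this order:

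1. Reconcile the event rates, so that one pair stands in words and symbols, with its direction clear. Redo the figures below if the symbols are not the intended pair.
2. Name the two-group contrast that the power refers to, for example mPG-SGA ≥ 3 vs 0–2, or NRS-2002 ≥ 3 vs < 3.
3. State the equal-group assumption behind 1,538, the attrition value used (50% reproduces it) and the expected exposed share.
4. Replace the flat 80% with power or detectable difference over that share. For 0.50 vs 0.40 at 50% attrition: about 54–80% over 16–80% exposed, or a detectable difference of about 10 to 13.5 points.
5. If the three mPG-SGA classes are mentioned, say only that this calculation does not power their pairwise comparisons at 80% and that they are supportive. Do not print 63% as a ceiling for class comparisons. If it is used, it should read that, for a 10-point difference at 769 evaluable, the weakest pair has at most about 63%.

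The cost is a rewritten paragraph and a less favourable power statement. No change to enrolment is proposed.

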57 primarily to identify modifiable risk factors associated with malnutrition-related morbidity and
58 mortality and assess the effectiveness of targeted nutritional interventions. The secondary objectives
59 include examining variations in nutritional status across cancer types and treatment modalities and
60 exploring how nutritional health interacts with psychological well-being, sleep quality, and physical
61 activity. Participants diagnosed with common malignancies across multiple hospitals undergo
62 baseline nutritional assessments within 48 hours of admission, followed by structured follow-ups at
63 1, 2, 3, 6, and 12 months and then annually for an additional four years to track nutritional changes
64 and key clinical endpoints (Riboli, 2001). Nutritional status, the primary exposure factor, is
65 classified via validated screening tools and dietary intake assessments. Patients are stratified on the
66 basis of malnutrition severity, dietary intake, and nutritional support status, with classifications
67 updated at each follow-up, to evaluate their associations with short- and long-term outcomes (**Fig.**
68 **1**).

[figure not shown]

Fig. 1. The workflow of the NCOM study.

Study Setting & Population

Study sites

The NCOM study was conducted across 11 tertiary hospitals in Xi'an, Shaanxi Province, China.

The participating institutions included Shaanxi Provincial Cancer Hospital; the First Affiliated

Hospital of Xi'an Jiaotong University; the Second Affiliated Hospital of Xi'an Jiaotong University; Shaanxi Provincial People's Hospital; the First Affiliated Hospital of the Fourth Military Medical University; the Second Affiliated Hospital of the Fourth Military Medical University; Shaanxi Provincial Chest Hospital; and the Affiliated Hospital of Northwest University Xi'an No.3 Hospital; Xi'an International Medical Center Hospital; The First Affiliated Hospital of Xi'an Medical University; The Second Affiliated Hospital of Xi'an Medical University.

Recruitment strategy

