Secondary analyses will investigate associations between nutritional status and psychosocial factors (e.g., EORTC QLQ-C30, HADS, PSQI) via paired t tests, mixed-effects models, and correlation analyses (Spearman or Pearson, depending on distribution).

To minimize bias and confounding factors, propensity score matching (PSM) will balance baseline differences between exposure groups. Multiple imputation will handle missing data to prevent systematic bias, and sensitivity analyses will exclude cases with extreme values, incomplete follow-ups, or protocol deviations.

Subgroup analyses will stratify findings by cancer type, treatment modality, and nutritional status category. Interaction terms are included in regression models to identify potential effect modifications, with exploratory analyses conducted if unexpected patterns arise.

By integrating multivariate modeling, survival analysis, repeated measures approaches, and

missing data imputation, this study ensures robust, high-quality, evidence-based insights into the impact of nutritional status on clinical outcomes and survival in cancer patients.

Informed Consent Process

Participation in this study is voluntary, and individuals may withdraw at any time without affecting their medical care. Before enrollment, participants and their families will receive detailed study information, including their purpose, methodology, potential risks, and benefits. A written informed consent form must be signed, confirming their understanding and voluntary participation.

The informed consent process will be conducted by trained research personnel, ensuring that participants fully understand the study's objectives and procedures; are aware of their right to withdraw at any time without impacting their current or future medical treatment; and have the opportunity to ask questions and receive clarifications before signing.

To accommodate diverse literacy levels, consent materials will be provided in clear, accessible language, with verbal explanations when needed. The informed consent form included both English and Chinese versions (**Supplementary File 1**).

Data Privacy & Confidentiality

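### Smoking, alcohol and tea are recorded as possible influences on both exposure and outcome, but the primary adjustment list omits them without a reason

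*Protocol*

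**What the plan says.** Three parts of the protocol bear on this.

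- **Why lifestyle data are collected** (Demographics & Clinical Data): "Lifestyle factors such as smoking, alcohol, and tea consumption are documented, given their potential influence on nutritional status and cancer progression". The same section covers medical history, but for a different purpose: "Medical history, including chronic conditions, previous diagnoses, medication use, and family history of malignancies, will also be recorded to assess genetic predispositions".
- **What the exposure is** (Study design): "Nutritional status, the primary exposure factor". Disease progression and death are among the follow-up categories under Short-Term & Long-Term Clinical Outcomes, and progression-free survival is analysed in the Statistical analysis plan section.
- **What the primary analysis adjusts for** (Statistical analysis plan section): regression models "adjusting for age, sex, cancer stage, treatment modality, socioeconomic status, and baseline Karnofsky Performance Status". The list is complete as worded; nothing marks it as a set of examples. Later in that section, "propensity score matching (PSM) will balance baseline differences between exposure groups", with no matching variables named and no stated link to the primary regression. The paragraph on Cox models names no adjustment set beyond time-dependent covariates where they apply.

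**The concern.** A variable that may affect both exposure and outcome is a candidate confounder, and that is the reason the protocol gives for recording smoking, alcohol and tea. The covariate list then leaves all three out. In an observational cohort the credibility of the nutrition effect rests on adjustment. If smokers or drinkers are unevenly spread over the nutritional groups and have a different prognosis, part of that difference would be credited to nutrition or would mask its effect.

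This is more than a detail left for a separate analysis plan. The protocol fixes the list itself, so an analysis plan that follows it would carry the omission forward, and extending the list after the data have been seen would be a post hoc choice.

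**Working it through.** **1. Comparison of the two lists.** The protocol contains no figure on this point to reproduce, so the first check is textual.

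| Variable | Stated link to exposure and outcome | In the primary list | In the propensity score |
|---|---|---|---|
| Smoking | Yes, as potential | No | Not stated |
| Alcohol | Yes, as potential | No | Not stated |
| Tea | Yes, as potential | No | Not stated |
| Chronic conditions | No; recorded for genetic predisposition | No | Not stated |

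The inconsistency holds for the first three rows. It does not hold for the fourth.

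**2. Possible size.** For one omitted binary factor, the ratio of the unadjusted to the true relative risk is

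B = [1 + pE(R − 1)] / [1 + pU(R − 1)],

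where pE and pU are the factor's prevalences in the exposed (malnourished) and unexposed groups, and R is its risk ratio for the outcome. The protocol gives none of these, so every input below is assumed.

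| pE | pU | R | Calculation | B |
|---|---|---|---|---|
| 35% | 30% | 1.2 | 1.07 / 1.06 | 1.01 |
| 40% | 30% | 1.5 | 1.20 / 1.15 | 1.04 |
| 50% | 30% | 1.5 | 1.25 / 1.15 | 1.09 |
| 50% | 30% | 2.0 | 1.50 / 1.30 | 1.15 |
| 60% | 30% | 2.0 | 1.60 / 1.30 | 1.23 |
| 30% | 30% | any | equal terms | 1.00 |
| 30% | 40% | 1.2 | 1.06 / 1.08 | 0.98 |
| 30% | 40% | 2.0 | 1.30 / 1.40 | 0.93 |

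These are crude factors. Adjustment for the six listed covariates may already remove part of the bias.

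**3. Is there a benchmark?** The Sample size section states event rates of 20% and 24% in words, a ratio of 0.24 / 0.20 = 1.20. An observed 1.20 would become 1.20 / 1.154 = 1.04 at B = 1.15, or 1.20 / 0.929 = 1.29 at B = 0.93. But the bracketed rates in the same sentence are 0.50 and 0.40, a ratio of 0.80. The target of about 1,538 follows from the bracketed pair: with "a two-sided significance level (α) of 0.05 and 80% power", equal groups (assumed) and unpooled variance, n = (1.960 + 0.842)² × (0.25 + 0.24) / 0.10² ≈ 384.6 per group, 769.2 in total, and 769.2 / 0.5 ≈ 1,538 at 50% attrition. The worded pair (pooled formula) needs 1,683 per group, 3,366 in total, and 4,809 to 6,732 after 30% to 50% attrition. So 1.20 is an illustration, not the effect behind the stated sample size.

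**4. Room in the model.** At 50% attrition about 769 participants are analysed. The mean worded rate of 22% gives 0.22 × 769 ≈ 169 events; the mean bracketed rate of 45% gives about 346. With an assumed 13 to 16 parameters after three added terms, the least favourable case is 169 / 16 ≈ 10.6 events per parameter. If coding needs five added terms instead of three, it is 169 / 18 ≈ 9.4.

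**The case against.** The best case for the protocol is that it speaks only of potential influence. That is a reason to collect data, not a finding that a confounding path stays open once stage, treatment, socioeconomic status and performance status are in the model. Matching may include lifestyle variables, and its covariates can properly be named in an analysis plan that is not shown.

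Much of this stands, and it rules out several stronger readings that a reader might infer:

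- **That known confounding stays in the main estimate.** The text supports only potential confounding that may remain, because the matching variables are open.
- **That chronic conditions are left out on the same footing.** Their stated purpose is different and no passage calls them a common cause. Severe comorbidity that may interfere with participation is also an exclusion criterion.
- **That the Cox models omit these variables.** The list is attached to the primary regression; the Cox covariates are not stated.
- **That smoking alone could produce a fifth to all of the planned contrast.** That reading compares factors of 1.04 to 1.23 with the 1.20 from rates that the same sentence contradicts. It considers only scenarios with more smoking among malnourished patients, and it reaches the whole contrast only in the most extreme one.

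What the objection does not remove is the mismatch between the stated reason for collection and a fixed list. The listed covariates do not measure smoking or drinking, which can vary within their levels, and nothing commits the matching to include them. Not knowing the direction of bias is a reason to adjust.

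**Conclusion.** The point holds in a limited form. The protocol names smoking, alcohol and tea as possible influences on both the primary exposure and an outcome, collects them, and omits them from its explicit primary adjustment set without explanation. Potential confounding may therefore remain in the primary estimate.

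The amount is not computable from the document. The illustrative range of about 0.93 to 1.23 rests wholly on assumed prevalences (30% to 60% in the exposed, 30% to 40% in the unexposed) and assumed risk ratios (1.2 to 2.0). It covers one binary factor and takes no account of the six covariates already listed. Bias in either direction, or none, is compatible with the protocol.

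**What to change.** In the Statistical analysis plan section:

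- Add baseline smoking status and alcohol consumption to the primary regression adjustment set. Add tea as well, or state why it is left out.
- State that the Cox and propensity score models use the same set.
- Fix the coding of the added variables before the data are examined.
- Chronic conditions may be added as a secondary or sensitivity covariate. A count of conditions would first need a definition, since the protocol has none.
- If the sponsor prefers to keep the present list, give the reason for leaving the lifestyle variables out.

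The lifestyle variables are already recorded at enrolment, so no new data collection is needed. The cost is a short change of text and a few more model parameters, which the event counts above can roughly carry even in the least favourable case.
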